These notes are recommendations for use in clinical studies. The use of standardized protocols for CT and MRI allows comparability both within and between different studies, irrespective of where the examination has been undertaken.

CT Scan

CT scans of chest and abdomen (including liver and adrenal glands) should be contiguous throughout all the anatomical regions of interest.

The most critical CT image acquisition parameters for optimal tumor evaluation using RECIST 1.1 are anatomic coverage, contrast administration, slice thickness, and reconstruction interval.

Anatomic coverage

Optimal anatomic coverage for most solid tumors is the chest, abdomen and pelvis. Coverage should encompass all areas of known predilection for metastases in the disease under evaluation and should additionally investigate areas that may be involved based on signs and symptoms of individual patients. Because a lesion later identified in a body part not scanned at baseline would be considered as a new lesion representing disease progression, careful consideration should be given to the extent of imaging coverage at baseline and at subsequent follow-up time points. This will enable better consistency not only of tumor measurements but also identification of new disease.

Intravenous contrast administration

Optimal visualization and measurement of metastases in solid tumors requires consistent administration (dose and rate) of intravenous contrast as well as timing of scanning. Typically, most abdominal imaging is performed during the portal venous phase and (optimally) about the same time frame after injection on each examination. An adequate volume of a suitable contrast agent should be given so that the metastases are demonstrated to best effect and a consistent method is used on subsequent examinations for any given patient. It is very important that the same technique be used at baseline and on follow- up examinations for a given patient. For patients who develop contraindications to contrast after baseline contrast CT is done, the decision as to whether non-contrast CT or MRI (enhanced or non-enhanced) should be performed should also be based on the tumor type, anatomic location of the disease and should be optimized to allow for comparison to the prior studies if possible. Each case should be discussed with the radiologist to determine if substitution of these other approaches is possible and, if not, the patient should be considered not evaluable from that point forward. Care must be taken in measurement of TLs on a different modality and interpretation of non-target disease or new lesions, since the same lesion may appear to have a different size using a new modality. Oral contrast is recommended to help visualize and differentiate structures in the abdomen.

If iodine contrast media is medically contraindicated at baseline or at any time during the course of the study, then the recommended methods are: CT thoracic examination without contrast and abdominal and pelvic MRI with contrast. If MRI cannot be performed then CT without

Date: July 24,2023

intravenous contrast is an option for the thorax, abdomen and pelvic examinations. For assessment of brain lesions MRI is the preferred method.

Slice thickness and reconstruction material

It is recommended that CT scans be performed at 5mm contiguous slice thickness, and this guideline presumes a minimum 5 mm thickness in recommendations for the measurable lesion definition. Exceptionally, particular institutions may perform medically acceptable scans at slice thicknesses greater than 5 mm. If this occurs, the minimum size of measurable lesions at baseline should be twice the slice thickness of the baseline scans.

All window settings should be included in the assessment, particularly in the thorax where lung and soft tissue windows should be considered. When measuring lesions, the TLs should be measured on the same window setting for repeated examinations throughout the study. All images from each examination should be included in the assessment and not "selected" images of the apparent lesion.

MRI Scan

MRI has excellent contrast, spatial and temporal resolution; however, there are many image acquisition variables involved in MRI, which greatly impact image quality, lesion conspicuity and measurement. Furthermore, the availability of MRI is variable globally. The modality used at follow-up should be the same as was used at baseline and the lesions should be measured/assessed on the same pulse sequence. Generally, axial imaging of the abdomen and pelvis with T1 and T2 weighted imaging along with gadolinium-enhanced imaging should be performed. The field of view, matrix, number of excitations, phase encode steps, use of fat suppression and fast sequences should be optimized for the specific body part being imaged as well as the scanner utilized. It is beyond the scope of this appendix to prescribe specific MRI pulse sequence parameters for all scanners, body parts and diseases. Ideally, the same type of scanner should be used, and the image acquisition protocol should be followed as closely as possible to prior scans. Body scans should be performed with breath-hold scanning techniques if possible.

For these reasons, CT is the imaging modality of choice.

FDG-PET scans

FDG-PET has gained acceptance as a valuable tool for detecting, staging and restaging several malignancies. If FDG-PET scans are included in a protocol, an FDG uptake period of 60 min prior to imaging has been decided as the most appropriate for imaging of patients with malignancy. Whole-body acquisition is important since this allows for sampling of all areas of interest and can assess if new lesions have appeared thus determining the possibility of interval progression of disease. Images from the base of the skull to the level of the mid-thigh should be obtained 60 min post injection. PET camera specifications are variable and manufacturer specific, so every attempt should be made to use the same scanner, or the same model scanner, for serial scans on the same patient. Whole-body acquisitions can be performed in either 2- or 3-dimensional mode with attenuation correction, but the method chosen should be consistent across all patients and serial scans in the clinical trial.

Date: July 24,2023

PET/CT scans

At present, low dose or attenuation correction CT portions of a combined PET–CT are of limited use in anatomically based efficacy assessments, and it is therefore suggested that they should not be substituted for dedicated diagnostic contrast enhanced CT scans for tumor measurements by RECIST 1.1. In exceptional situations, if a site can document that the CT performed as part of a PET–CT is of identical diagnostic quality to a diagnostic CT (with IV and oral contrast) then the CT portion of the PET–CT can be used for RECIST measurements. However, this is not recommended because the PET portion of the CT introduces additional data that may bias an investigator if it is not routinely or serially performed.

REFERENCES

Eisenhauer et al 2009

Date: July 24,2023

Appendix G ACTIONS REQUIRED IN CASE OF COMBINED INCREASE OF AMINOTRANSFERASE AND TOTAL BILIRUBIN-HY'S LAW

Introduction

During the course of the study the Investigator will remain vigilant for increases in liver biochemistry. The investigator is responsible for determining whether a patient meets potential Hy's Law (PHL) criteria at any point during the study.

The Investigator participates, together with Dizal clinical project representatives, in review and assessment of cases meeting PHL criteria to agree whether Hy's Law (HL) criteria are met. HL criteria are met if there is no alternative explanation for the elevations in liver biochemistry other than Drug Induced Liver Injury (DILI) caused by the Investigational Medicinal Product (IMP).

The Investigator is responsible for recording data pertaining to PHL/HL cases and for reporting Adverse Events (AE) and Serious Adverse Events (SAE) according to the outcome of the review and assessment in line with standard safety reporting processes.

Definitions

Potential Hy's Law (PHL)

Aspartate Aminotransferase (AST) or Alanine Aminotransferase (ALT) ≥ 3 x Upper Limit of Normal (ULN) and Total Bilirubin (TBL) ≥ 2 x ULN at any point during the study irrespective of an increase in Alkaline Phosphatase (ALP).

Hy's Law (HL)

AST or ALT \geq 3 x ULN and TBL \geq 2 x ULN, where no other reason, other than the IMP, can be found to explain the combination of increases, e.g., elevated ALP indicating cholestasis, viral hepatitis, another drug.

Identification of potential Hy's law cases

In order to identify cases of PHL it is important to perform a comprehensive review of laboratory data for any patient who meets any of the following identification criteria in isolation or in combination:

- ALT $\geq 3x$ ULN
- AST $\geq 3x$ ULN
- TBL > 2x ULN

The Investigator will without delay review each new laboratory report and if the identification criteria are met will:

Notify the Dizal representative

Date: July 24,2023

• Determine whether the patient meets PHL criteria (see Section Definitions of this Appendix for definition) by reviewing laboratory reports from all previous visits

Promptly enter the laboratory data into the laboratory CRF

Follow-up

Potential Hy's Law Criteria not met

If the patient does not meet PHL criteria the Investigator will:

- Inform the Dizal representative or delegate that subject has not met PHL criteria.
- Perform follow-up on subsequent laboratory results according to the guidance provided in the Clinical Study Protocol.

Potential Hy's Law Criteria met

If the patient does meet PHL criteria the Investigator will:

- Determine whether PHL criteria were met at any study visit prior to starting study treatment in the presence of liver metastases (See Section Actions required when potential Hy's law criteria are met before and after starting study treatment)
- Notify the Dizal representative who will then inform the central Study Team
- The Study Physician contacts the Investigator, to provide guidance, discuss and agree an approach for the study patients' follow-up and the continuous review of data. Subsequent to this contact the Investigator will:
- Monitor the patient until liver biochemistry parameters and appropriate clinical symptoms and signs return to normal or baseline levels, or as long as medically indicated
- Investigate the etiology of the event and perform diagnostic investigations as discussed with the Study Physician
- Complete the three Liver CRF Modules as information becomes available
- If at any time (in consultation with the Study Physician) the PHL case meets serious criteria, report it as an SAE using standard reporting procedures

Review and Assessment of potential Hy's law cases

The instructions in this Section should be followed for all cases where PHL criteria are met.

No later than 3 weeks after the biochemistry abnormality was initially detected, the Study Physician contacts the Investigator in order to review available data and agree on whether there is an alternative explanation for meeting PHL criteria other than DILI caused by the IMP. The Dizal Medical Science Director and Global Safety Physician will also be involved in this review together with other subject matter experts as appropriate.

Clinical Study Protocol Drug Substance: DZD9008 Protocol No.: DZ2019E0001

Edition Number: 12.0 Date: July 24,2023

According to the outcome of the review and assessment, the Investigator will follow the instructions below.

If there **is** an agreed alternative explanation for the ALT or AST and TBL elevations, a determination of whether the alternative explanation is an AE will be made and subsequently whether the AE meets the criteria for a SAE:

- If the alternative explanation is **not** an AE, record the alternative explanation on the appropriate CRF
- If the alternative explanation is an AE/SAE, record the AE/SAE in the CRF accordingly and follow the standard processes
- If it is agreed that there is **no** explanation that would explain the ALT or AST and TBL elevations other than the IMP:
- Report an SAE (report term 'Hy's Law') according to Dizal standard processes.
- The 'Medically Important' serious criterion should be used if no other serious criteria apply
- As there is no alternative explanation for the HL case, a causality assessment of 'related' should be assigned.

If, there is an unavoidable delay, of over 3 weeks, in obtaining the information necessary to assess whether or not the case meets the criteria for HL, then it is assumed that there is no alternative explanation until such time as an informed decision can be made:

- Report an SAE (report term 'Potential Hy's Law') applying serious criteria and causality assessment as per above
- Continue follow-up and review according to agreed plan. Once the necessary supplementary information is obtained, repeat the review and assessment to determine whether HL criteria are met. Update the SAE report according to the outcome of the review

Actions required when potential Hy's law criteria are met before and after starting study treatment

This section is applicable to patients who meet PHL criteria on study treatment having previously met PHL criteria at a study visit prior to starting study treatment.

At the first on study treatment occurrence of PHL criteria being, even if there has been no significant change the patient's condition[#] compared with pre-study treatment visits, the Investigator will:

• Notify the Dizal representative who will inform the central Study Team.

Date: July 24,2023

• Follow the subsequent process described is Section Potential Hy's Law Criteria met of this Appendix.

[#] A 'significant' change in the patient's condition refers to a clinically relevant change in any of the individual liver biochemistry parameters (ALT, AST or total bilirubin) in isolation or in combination, or a clinically relevant change in associated symptoms. The determination of whether there has been a significant change will be at the discretion of the Investigator, this may be in consultation with the Study Physician if there is any uncertainty.

Actions required for repeat episodes of potential Hy's law

This section is applicable when a patient meets PHL criteria on study treatment and has already met PHL criteria at a previous on study treatment visit.

The requirement to conduct follow-up, review and assessment of a repeat occurrence(s) of PHL is based on the nature of the alternative cause identified for the previous occurrence.

The investigator should determine the cause for the previous occurrence of PHL criteria being met and answer the following question:

• Was the alternative cause for the previous occurrence of PHL criteria being met chronic or progressing malignant disease or did the patient meet PHL criteria prior to starting study treatment and at their first on study treatment visit as described in Section Actions required when potential Hy's law criteria are met before and after starting study treatment?

If No: follow the process described in Section Potential Hy's Law Criteria met of this Appendix. If Yes:

Determine if there has been a significant change in the patient's condition# compared with when PHL criteria were previously met

- If there is no significant change no action is required
- If there is a significant change follow the process described in Section Potential Hy's Law Criteria met of this Appendix
- # A 'significant' change in the patient's condition refers to a clinically relevant change in any of the individual liver biochemistry parameters (ALT, AST or total bilirubin) in isolation or in combination, or a clinically relevant change in associated symptoms. The determination of whether there has been a significant change will be at the discretion of the Investigator, this may be in consultation with the Study Physician if there is any uncertainty.

References

FDA Guidance for Industry (issued July 2009) 'Drug-induced liver injury: Premarketing clinical evaluation':

http://www.fda.gov/downloads/Drugs/GuidanceComplianceRegulatoryInformation/Guidances/UCM174090.pdf.

Date: July 24,2023

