5.3 Discontinuation of investigational product and withdrawal from the study

Patients may withdraw from the study at any time, without prejudice to further treatment and independent of any decision concerning participation in other aspects of the main study. Procedures for withdrawal from the exploratory research are outlined in Section 5.3.2.

Patients may be discontinued from investigational product in the following situations:

- Patient decision. The patient is at any time free to withdraw his/her participation in the study, without prejudice
- Adverse events

• Severe non-compliance to this protocol as judged by the investigator and/or Study Team

- Confirmed disease progression as per RECIST 1.1, unless, in the opinion of the investigator, the patient is still deriving clinical benefit. For France and Canada only: fulfil the following criteria: (a) Absence of clinical symptoms and signs of disease progression (including clinically significant worsening of laboratory values); (b) Stable ECOG PS; (c) Absence of rapid progression of disease or of progressive tumor at critical anatomical sites that requires urgent alternative medical intervention; (d) Investigators must inform subjects that this practice is not considered standard in the treatment of cancer.
- Patients incorrectly initiated on investigational product (Section 5.3.1)
- Pregnancy

Patients who withdraw from the study but are evaluable for safety assessment in Part A escalation will not be replaced. Any patient that is not evaluable in Part A escalation will be replaced to ensure a minimum number of evaluable patients. Once study medication is permanently discontinued it cannot be restarted.

In Part A expansion and Part B, any patient who discontinues study treatment for reasons other than disease progression should have RECIST assessment performed as scheduled in Table 13 and Table 14 of the protocol until disease progression is documented or death occurs, or consent is withdrawn. Study procedure related SAEs and anti-cancer treatment must be captured until the patient no longer has RECIST 1.1 tumor assessment (disease progression or permanent withdrawal from the study).

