6.3.6.2 Progression follow up

Patients who discontinue DZD9008 for reasons other than progression will continue RECIST 1.1 assessments on Cycle 3 Day1 (\pm 7 days), then every 6 weeks (\pm 1 week) until objective disease progression.

Details of concomitant medications (including any subsequent cancer therapy) should continue to be collected as detailed in the study plan up to the 28-day follow up visit. Beyond the 28-day follow up visit only subsequent cancer therapy and new SAEs due to study procedures should be collected.

Date: July 24,2023

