6.8 Anti-tumor efficacy

6.8.1 Tumor assessments

6.8.1.1 Imaging assessment

RECIST 1.1 criteria will be used to assess tumor response to treatment by determining Objective Response rate (ORR), Disease Control Rate (DCR), Duration of Response (DOR) and Progression Free Survival (PFS). The RECIST 1.1 guidelines for measurable, non-measurable, target and non-target lesions and the objective tumor response criteria (complete response, partial response, stable disease or progression of disease) will be used for the assessment of tumors according to Appendix F.

Imaging assessments will be performed using CT scan or MRI to assess extracranial lesions, such as chest, abdomen (including liver and adrenal glands). MRI is the preferred method for analyzing the brain lesion if brain metastasis presents at baseline (within 28 days of treatments start, ideally as close as possible to the start of study treatment), on Cycle 3 Day 1 (\pm 7 days) and then every 6 weeks \pm 7 days until objective disease progression or withdrawal from study. Contrast-enhanced CT can be used if MRI is not feasible. In addition, additional areas should be investigated based on the signs and symptoms of the patient. Any other sites at which new disease is suspected should also be appropriately imaged. If an unscheduled assessment is performed and the patient has not progressed, every attempt should be made to perform the subsequent assessments at their scheduled visits.

Categorization of objective tumor response assessment will be based on the RECIST 1.1: CR (complete response), PR (partial response), SD (stable disease) and PD (progression of disease). Target lesion (TL) progression will be calculated in comparison to when the tumor burden is at a minimum (i.e. smallest sum of diameters previously recorded on study). In the absence of progression, tumor response (CR, PR, SD) will be calculated in comparison to the baseline

Date: July 24,2023

tumor measurements obtained before starting treatment. For objective response rate (ORR), a visit response of CR or PR must be confirmed by a later scan conducted at the next scheduled visit and no less than 4 weeks after the initial visit response of CR or PR.

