If the Investigator is in doubt as to whether progression has occurred, particularly with response to NTL (non-target lesion) or the appearance of a new lesion, it is advisable to continue treatment until the next scheduled assessment or sooner if clinically indicated and reassess the patient's status. If repeated scans confirm progression, then the date of the initial scan should be declared as the date of progression.

To achieve 'unequivocal progression' on the basis of non-target disease, there must be an overall level of substantial worsening in non-target disease such that, even in presence of SD or PR in target disease, the overall tumor burden has increased sufficiently to merit discontinuation of therapy. A modest 'increase' in the size of one or more non-target lesions is usually not sufficient to quality for unequivocal progression status.

It is important to follow the assessment schedule as closely as possible. Please refer to the study plan (Table 11, Table 12, Table 13, Table 14).

All images for RECIST 1.1 assessment will be reviewed at site. Duplicates will be collected on an ongoing basis and stored by a Sponsor appointed representative, and sent for Independent Review Committee.

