This appendix details the implementation of RECIST (Response Evaluation Criteria in Solid Tumors) 1.1 guidelines (Eisenhauer et al 2009) for the study with regards to investigator assessment of tumor burden including protocol-specific requirements for this study.

Definition of measurable, non-measurable, target and non-target lesions

Patients with at least one lesion measurable that can be accurately assessed at baseline by computerized tomography (CT), magnetic resonance imaging (MRI) or plain X-ray should be included in this study.

Measurable lesions

At least one lesion, not previously irradiated, that can be accurately measured at baseline as \geq 10 mm in the longest diameter (except lymph nodes which must have short access \geq 15mm) with computered tomography (CT) or magnetic resonance imaging (MRI) which is suitable for accurate repeated measurements.

Non-measurable lesions

- All other lesions, including small lesions (longest diameter < 10 mm or pathological lymph nodes with ≥ 10 mm to < 15 mm short axis at baseline. Nodes with < 10 mm short axis are considered non-pathological and should not be recorded as non-target lesions (NTLs)
- Truly non-measurable lesions include the following: bone lesions, leptomeningeal disease, ascites, pleural / pericardial effusion, inflammatory breast disease, lymphangitic involvement of skin or lung, abdominal masses/abdominal organomegaly identified by physical examination that are not measurable by CT or MRI
- Previously irradiated lesions as localized post-radiation changes, which affect lesion sizes, may occur. Therefore, lesions that have been previously irradiated will not be considered measurable and should be selected as NTLs at baseline and followed up as part of the NTL assessment
- Skin lesions assessed by clinical examination
- Brain metastasis

Special cases

• Lytic bone lesions or mixed lytic-blastic lesions, with identifiable soft tissue components, can be considered measurable if the soft tissue component meets the definition of measurability. Blastic lesions are considered non-measurable.

Date: July 24,2023

Cystic metastases can be considered measurable lesions if they meet the criteria for
measurability from a radiological point of view, but if non-cystic lesions are present in
the same patient, these non-cystic lesions should be selected as the target lesions (TLs).

Target lesions

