FDG-PET (fluorodeoxyglucose positron emission tomography) scans may be used as a method for identifying new lesions, according with the following algorithm: New lesions will be recorded where there is positive FDG uptake (defined as when an uptake greater than twice that of the surrounding tissue is observed) not present on baseline FDG-PET scan or in a location corresponding to a new lesion on CT/MRI at the same follow-up visit. If there is no baseline FDG-PET scan available, and no evidence of new lesions on CT/MRI scans then follow-up CT/MRI assessments should be continued, scheduled as per protocol or clinical indicated, in order to confirm new lesions.

Tumor response evaluation

Schedule of evaluation

CT examinations of the chest and abdomen (including liver adrenal glands) will be used to assess tumor burden at baseline and follow-up visits. CT examination with intravenous contract media administration is the preferred method. MRI should be used where CT is no feasible or it is medically contra-indicated.

Baseline tumor assessments should encompass all areas of known predilection for metastases in the disease under evaluation and should additionally investigate areas that may be involved based on signs and symptoms of individual patients and should be performed no more than 28 days before the start of study treatment. Follow-up assessments should be performed every 6 weeks (\pm 7 days) after the start of treatment until discontinuation of study treatment or withdrawal of consent. Any other sites at which new disease is suspected should also be adequately imaged at follow-up. Following the 24 month DCO, tumor assessment will be performed in accordance with clinical practice with the exception of those in the Phase I first line expansion cohort. For the Phase I first line expansion cohort RECIST 1.1 assessments will continue every 12 weeks (\pm 7 days) until disease progression.

If an unscheduled assessment was performed and the patient has not progressed, every attempt should be made to perform the subsequent assessments as their scheduled visits. This schedule is to be followed in order to minimize any unintentional bias caused by some patients being assessed at different frequency than other patients.

Target lesions

Documentation of target lesions

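### Appendix F ends tumour scans when study treatment stops, while the protocol body and the SAP continue them to objective progression

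*Protocol*

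**What the plan says.** Appendix F describes itself as implementing RECIST 1.1 "with regards to investigator assessment of tumor burden including protocol-specific requirements for this study". Its Schedule of evaluation sets scans every 6 weeks (±7 days) "after the start of treatment until discontinuation of study treatment or withdrawal of consent". Progression is not named as an end point. The same paragraph goes on to later follow-up: "Following the 24 month DCO, tumor assessment will be performed in accordance with clinical practice", with a 12-weekly schedule to progression for the first-line expansion cohort.

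The protocol body differs. Section 5.3, for Part A expansion and Part B, says "any patient who discontinues study treatment for reasons other than disease progression should have RECIST assessment performed as scheduled", ending at progression, death or withdrawn consent. Section 6.3.6.2 says "Patients who discontinue DZD9008 for reasons other than progression will continue RECIST 1.1 assessments", ending at objective progression. Section 6.8.1.1 runs scans "until objective disease progression or withdrawal from study". SAP 2.2 repeats the rule of 6.3.6.2. The symptomatic-deterioration paragraph of Appendix F also keeps patients who stop treatment without objective progression on scans until progression is seen.

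**The concern.** The scan interval agrees everywhere; the end of scanning does not. The conflict falls on one group: patients who stop DZD9008 without progression, for example for toxicity.

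The analysis rules assume that these patients are still scanned. The best-response definition in Protocol 7.5.1 applies whether or not the drug was stopped. The primary estimand in SAP 2.1.1 treats discontinuation for reasons other than IRC-assessed progression under a treatment-policy strategy. Protocol 7.5.2 and row 4 of SAP Table 2 use data after discontinuation for PFS.

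Those rules are sound. The risk is at data collection: a scan never taken cannot enter the analysis. Although Appendix F is written for investigator assessment, 6.8.1.1 sends duplicates of the site's images to the IRC, so a missing site scan is also missing from the IRC-assessed primary endpoint.

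**Working it through.** No figure in the plan bears on this point, so the check compares the passages and then traces patients through the SAP rules.

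**1. When do scans end for a patient who stops the drug without progression?**

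| Place | Scans end at |
|---|---|
| Appendix F, Schedule of evaluation | Treatment discontinuation or withdrawn consent |
| Protocol 5.3 | Progression, death or withdrawn consent |
| Protocol 6.3.6.2 | Objective progression |
| Protocol 6.8.1.1 | Objective progression or withdrawal from study |
| SAP 2.2 | Objective progression |
| Appendix F, Symptomatic deterioration | Objective progression |

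All five other places conflict with the first row.

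**2. Scan days.** With 21-day cycles, Cycle 3 Day 1 is Day 2 × 21 + 1 = 43. The next scheduled scans are Day 43 + 42 = 85 and Day 85 + 42 = 127. SAP 4.2.1 requires at least 28 days between the two scans of a confirmed response. SAP Table 1 also accepts PR, then SD or NE, then PR, so confirmation can come 127 − 43 = 84 days after first response.

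**3. Hypothetical patients** (alive, no new anticancer therapy, no off-schedule scan):

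| Drug stops | Scans if 5.3 and 6.3.6.2 are followed | Result if the Appendix F sentence is followed |
|---|---|---|
| Before Day 43 | PR Day 43, PR Day 85: confirmed PR | No post-baseline scan, no response to count; PFS censored at first dose (Table 2, row 1.1) |
| Between Day 43 and Day 85, after PR on Day 43 | PR Day 85: confirmed PR | PR unconfirmed, not a responder; PFS censored at Day 43 |
| Between Day 85 and Day 127, after PR then SD | PR Day 127: confirmed PR | PR unconfirmed, not a responder; PFS censored at Day 85 |
| After Day 85, PR already confirmed | Followed to progression | ORR unchanged; PFS and DoR censored at Day 85, so DoR is (85 − 43 + 1)/30.4375 = 1.4 months, censored |

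ORR is therefore exposed before first response as well as between response and confirmation.

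**4. Deaths.** Rows 6 and 7 of SAP Table 2, with the footnote, keep a death as a PFS event when it falls within 98 days of the last evaluable scan. For a last scan on Day 85 that means up to Day 85 + 98 = 183. A later death is censored at Day 85 in the primary PFS analysis and counted in the sensitivity analysis. The end of DoR follows PFS. A patient with no post-baseline scan remains an event if death comes within 13 weeks of first dose (row 8).

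**5. Size.** In an arm of 103, each lost confirmed response lowers ORR by 1/103 = 0.97 percentage points. The number lost cannot be derived from the documents.

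**The case against.** The strongest reply is that nobody would be misled. Sections 5.3 and 6.3.6.2 address exactly this patient, the RECIST row of Table 14 points to 6.8.1, and 6.8.1.1 sends sites to the study plan for timing: "It is important to follow the assessment schedule as closely as possible. Please refer to the study plan". For harm to occur, a site must prefer a general appendix sentence to two specific sections. This stands and limits the severity.

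One can also read the sentence as an on-treatment schedule, with 6.3.6.2 covering what follows. The wording carries no such limit, and the paragraph goes on to set scan rules after the 24-month data cut-off, so it reads as a complete schedule.

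Some stronger readings are tempting but unsupported:

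- That Appendix F makes its stopping point mandatory through "This schedule is to be followed in order to minimize any unintentional bias". That sentence continues about patients being assessed at different frequencies. It does not concern when scans end. The pointers to Appendix F in the Table 14 footnote and SAP 4.2.1 sit beside text on scan modality and response definitions, so they add little.
- That 5.1.5, 5.3.2 and 6.8.1.1 together end tumour follow-up after toxicity. Section 5.3.2 concerns patients who withdraw consent and does not supply that link. What remains is looser: 5.1.5 speaks of withdrawal from the study for unresolved toxicity, and 6.8.1.1 ends scans at withdrawal from study.
- That all lost information is beyond recovery. Protocol 7.5 gives the IRC every scan, including unscheduled ones, so scans taken off schedule could still count.

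**Conclusion.** The contradiction is real, is in current text and should be corrected. It is one appendix sentence against a consistent protocol body and SAP, so it is a conduct risk and not a flaw in the design or the analysis rules.

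The consequence is conditional on a site following Appendix F for a patient who stops the drug without progression. For that patient, responses first seen or confirmed after drug stop are lost from confirmed ORR. Without documented progression, PFS and DoR are censored at the last on-treatment scan, or PFS at first dose if there was none, except where death falls within the limits of SAP Table 2.

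A reader might infer a loss of power for the primary test. The documents do not support a figure: it would need an assumed proportion of responders losing confirmation, and none is given. The severity rests on the contradiction and on the endpoint it touches.

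**What to change.** In Appendix F, Schedule of evaluation, reword the end of scanning so that patients who stop DZD9008 without progression continue on schedule until objective progression, death or withdrawal of consent, as 5.3 and 6.3.6.2 already require. Because 5.3 is limited to Part A expansion and Part B while Appendix F has no such limit, the new wording should state its scope.

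Two things need care:

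- Leave the sentences on scanning after the 24-month data cut-off unchanged.
- Do not remove scans from patients treated beyond progression. Section 5.3 allows such treatment, the present Appendix F sentence keeps those patients on scans until treatment stops, and 6.8.1.1 ends scans at progression. SAP 7.1 anticipates IRC visits after investigator-assessed progression. Any change here must first be reconciled with 6.8.1.1.

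As a minor item, reconcile the withdrawal wording in 5.1.5 with that in 6.8.1.1, so that stopping treatment for toxicity is not read as ending tumour follow-up. No toxicity or treatment-stopping rule changes.

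The cost is one sentence, one wording reconciliation and a clarification letter to sites. No scans are added beyond those that 5.3 and 6.3.6.2 already require.
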